7.2 Methods and Timing for Assessing, Recording, and Analyzing Safety Parameters

Weekly symptom monitoring is standard practice for monitoring safety during treatment of PTSD. [name] will review AEs on an ongoing basis as they occur and in aggregate, along with [name], at the end of each group.

7.3 Adverse Events and Serious Adverse Events

An **adverse event (AE)** will be defined as any unfavorable and unintended diagnosis, symptom, sign (including an abnormal laboratory finding), syndrome or disease which either occurs during the study, having been absent at baseline, or if present at baseline, appears to worsen. Adverse events are to be recorded regardless of their relationship to the study intervention.

A **serious adverse event (SAE)** will be defined as any untoward medical occurrence that results in death, is life threatening, requires inpatient hospitalization or prolongation of existing hospitalization, results in persistent or significant disability/incapacity, or is a congenital anomaly.

Expected psychiatric AEs will be solicited through weekly assessments and therapist inquiries. Other types of medical AEs, which are very unlikely to be related to the study interventions, will be unsolicited but could be noted by therapists during weekly inquiries about how each participant is doing.

Information on all adverse events will be recorded immediately in AE forms. All adverse events occurring during the study period will be recorded. The clinical course of each event will be followed until resolution, stabilization, or until it has been determined that the study treatment or participation is not the cause. Serious adverse events (SAEs) that are still ongoing at the end of the study period will be followed up to determine the final outcome. Any SAE that occurs after the study period and is considered to be possibly related to the study treatment or study participation will be recorded and reported immediately. Minimum information required for each AE includes type of event, duration (start and end dates), severity, seriousness, causality to study intervention, action taken, and outcome.

Evaluating Adverse Events. Assessment will include the intensity (severity) of the event and the relationship to study intervention. Severity of AEs will be graded using the following criteria as guidelines: 1. Mild: Nuisance, barely noticeable. 2. Moderate: Uncomfortable, troublesome symptoms not significantly interfering with daily activities or sleep. 3. Severe: Symptoms significantly interfere with daily activities or sleep. The relationship of the AE to the study will be specified using the following definitions: 1. Not Related: Concomitant illness, accident or event with no reasonable association with treatment. 2. Unlikely: The reaction has little or no temporal sequence from participation and/or a more likely alternative etiology exists. 3. Possibly Related: The reaction follows a reasonable temporal sequence from participation and follows a known response pattern to the intervention; the reaction could have been produced by the study intervention or could have been produced by the subject's clinical state or by other modes of treatment administered to the subject. 4. Probably Related: The reaction follows a reasonable temporal sequence from participation and cannot be reasonably explained by the known characteristics of the subject's clinical state. 5. Definitely Related: The reaction follows a reasonable temporal sequence from participation and cannot be explained by the known characteristics of the subject's clinical state.

7.4 Reporting Procedures

Reporting of AEs. Negative events that occur during study involvement do not constitute adverse events unless they lead to physical harm (in which case the injury is the AE) or deterioration of mental health functioning (in which case the symptoms are the AE). Negative events that may potentially affect response to the intervention or study involvement should be reported as AEs. Examples might include legal problems or traumatic events.

An AE form will be placed in the participant folder. This form is cumulative and captures adverse events of a single participant throughout the study. The study therapist will document each AE reported on the form. The study coordinator will periodically review and compile the information into summary or table form for reporting to both the Independent Monitoring Committee (IMC) and the VASDHS IRB at the time of continuing review.

Reporting of Serious Adverse Events and Unanticipated Problems. An AE occurring in a participant enrolled in a research study is serious if it results in any of the following outcomes: death, a life-threatening adverse drug experience, inpatient hospitalization or prolongation of existing hospitalization, a persistent or significant disability/incapacity, or is a congenital anomaly/birth defect. Examples of possible UPRs for psychotherapeutic interventions:

1. Psychosis or mania
2. New onset or clinically significant exacerbation of an Axis I disorder
3. Suicide and suicide attempts.

Any study-related unanticipated problem posing risk of harm to subjects or others and any serious adverse event regardless of relatedness will be reported immediately to the PI, the VASDHS IRB within 10 days using the VASDHS Human Research Protections Program form REPORT OF UNANTICIPATED PROBLEM INVOLVING RISK TO SUBJECT OR OTHERS (dated 7/9/12), and NCCAM according to requirements.

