7.1 Specification of Safety Parameters

Distress will be identified by a clinically significant increase in total score on the AUDIT, PHQ-9 or PCL or by increases on specific items, such as PHQ item 9 which queries suicidality.

At each contact with the participant, the assessor or therapist will seek information on AEs by specific questioning. Information on all AEs will be recorded immediately in the study records and VA CPRS. All AEs occurring during the study period will be recorded on AE forms.

The clinical course of each event will be followed until resolution, stabilization, or until it has been determined that the study treatment or participation is not the cause.

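### Section 7.4 gives opposite rules on whether a negative life event is an AE, and 7.1 and 7.3 disagree on whether non-psychiatric medical AEs are asked about

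*Combined protocol and SAP*

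**What the plan says.** **What counts as an AE.** Section 7.3 defines an AE as "any unfavorable and unintended diagnosis, symptom, sign (including an abnormal laboratory finding), syndrome or disease" that is new during the study or worse than at baseline. Section 7.4 then deals with negative events in two consecutive sentences. The first reads "Negative events that occur during study involvement do not constitute adverse events unless they lead to physical harm", or a decline in mental health; the resulting injury or symptoms are then the AE. The second reads "Negative events that may potentially affect response to the intervention or study involvement should be reported as AEs", followed by "Examples might include legal problems or traumatic events".

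**How AEs are found.** Section 7.1 says that at each contact "the assessor or therapist will seek information on AEs by specific questioning". Section 7.3 splits the task. "Expected psychiatric AEs will be solicited through weekly assessments and therapist inquiries", whereas other medical AEs "will be unsolicited but could be noted by therapists during weekly inquiries about how each participant is doing".

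**What must be reported.** Under 7.3 an SAE includes any untoward medical occurrence that "results in death, is life threatening, requires inpatient hospitalization or prolongation of existing hospitalization". Under 7.4 every SAE goes to the principal investigator, the IRB and NCCAM, related or not. The study therapist fills in a cumulative AE form for each participant, and the coordinator compiles these forms for the Independent Monitoring Committee and the IRB.

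**The concern.** A therapist holding the AE form has two instructions for the same event. A participant with a legal problem, and no injury or worsening, has no AE under the first sentence of 7.4 and has one under the second. The phrase about possible effects on response or involvement sets no threshold, so inclusion is a matter of judgement. In Phase 2 that judgement is made by someone who knows the arm, since 6.2.3 exempts the therapists from blinding.

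The collection rules raise a different problem. If therapists follow 7.3, nothing prompts a participant to mention a medical admission, yet 7.4 requires that admission to be reported as an SAE.

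At stake are the comparability of AE counts across therapists and arms, and the completeness of SAE reporting. The primary CAPS-5 outcome is not affected.

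**Working it through.** The documents give no AE rate, count or threshold, so there is no figure to reproduce. The check is a comparison of the sections, with one piece of arithmetic for scale.

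**Step 1: apply each rule to the same event.**

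| Event | 7.4, first sentence | 7.4, second sentence | 7.3 definition |
|---|---|---|---|
| Legal problem, no injury or worsening | Not an AE | AE if it may affect response or involvement | Not an AE |
| Imprisonment, no injury or worsening (participant withdrawn under 4.2 and 5.3.3) | Not an AE | AE, since involvement ends | Not an AE |
| Traumatic event, no injury or worsening | Not an AE | AE if it may affect response or involvement | Not an AE |
| Any of these, followed by injury or psychiatric worsening | The injury or symptoms are the AE | AE | The injury or symptoms are an AE |

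The rules disagree in the first three rows. In the fourth, the participant has an AE under all of them. The severity grades in 7.3 do not help with the first three rows, because they largely describe symptoms and their interference with activities or sleep.

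**Step 2: compare the collection rules by type of AE.**

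| Type | 7.1 | 7.3 | Result |
|---|---|---|---|
| Expected psychiatric | Asked at each contact | Solicited weekly | Agree |
| Other medical | Asked at each contact | Unsolicited | Conflict |

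Nothing else in the plan closes the second row. The weekly safety measures in Section 7 cover alcohol consumption, depression and PTSD symptoms, not admissions. The schedules in 6.1 have no AE row.

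**Step 3: trace the route to SAEs.** A negative event that ends in admission for injury or psychiatric deterioration is an AE under the first sentence of 7.4 as well as the second. The negative-event conflict therefore adds or removes essentially no SAEs. The route that remains is Step 2: a non-psychiatric admission about which 7.3 does not require anyone to ask.

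**Step 4: scale.** Section 9.1 gives Phase 2 two groups per arm with 6 to 12 participants in each.

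- Participants per arm: 2 × 6 = 12 to 2 × 12 = 24; about 40 / 2 = 20 at the planned size.
- Shift in one arm's proportion with an AE when one participant is reclassified: 1/12 = 8.3, 1/20 = 5.0, 1/24 = 4.2 percentage points.

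The number of participants who would be reclassified cannot be derived from the documents.

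**The case against.** The second sentence of 7.4 may be meant as a logging instruction: such events are not AEs by definition but go on the AE form because they could explain a change in symptoms. Likewise, 7.3 can be read as a specific exception to the general rule in 7.1, and therapists do ask each week how participants are doing. Section 7.6 also points to a separate Data and Safety Monitoring Plan, not among the documents reviewed, which might settle what is tabulated. These readings are reasonable, but the protocol states none of them. The form is what the coordinator compiles, so a logged life event still reaches the AE table unless something says otherwise. A general weekly inquiry is also not a question about admissions.

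A reader might infer more than the text supports:

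- **That all AEs are both asked about and not asked about.** Psychiatric AEs, the ones the protocol expects, are solicited under both sections.
- **That the 7.4 conflict changes SAE counts.** Step 3 shows that it hardly can.
- **That a particular share of participants is affected.** No document gives a rate of legal problems or traumatic events.
- **That the safety summary cannot be interpreted.** Type, severity and causality are recorded for every AE, and the causality scale has an unrelated category that expressly covers accidents and events, so misplaced life events could be separated later. Traumatic events also appear on the Life Events Checklist, listed at sessions 1 to 8 in Phase 1 and used after treatment in Phase 2. AEs are not an outcome in 9.5, no between-arm AE test is planned in 9.6, and 9.4 has no interim analyses or stopping rules.
- **That recording rests wholly on an unblinded therapist.** Under 7.1 the assessor, blind in Phase 2, also seeks AEs, although the therapist completes the form.

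**Conclusion.** Two inconsistencies stand. First, 7.4 gives opposite answers for a legal problem or traumatic event without harm, and its second answer lies outside the 7.3 definition. Second, 7.1 and 7.3 disagree on whether non-psychiatric medical AEs are asked about, while 7.4 requires every SAE to be reported.

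The consequences are limited. The AE table sent to the monitoring committee and the IRB depends on which sentence is applied, by 4.2 to 8.3 percentage points per reclassified participant in a Phase 2 arm of 24 down to 12. A medical admission can go unrecorded. The per-participant shift assumes only the planned group sizes; the total effect is unknown. The definitional conflict applies in both phases, but an imbalance between randomized arms can arise only in Phase 2. No planned inference turns on these counts. The text should be corrected because it is wrong as written and cheap to repair.

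**What to change.** 1. **Section 7.4.** Make the 7.3 definition the only AE definition and bring both negative-event sentences into line with it. Log life events without harm, such as legal problems or traumatic events, on a separate line of the same form, and state that this line is not counted in the AE table. An injury or symptom that follows is recorded as an AE in the usual way.
2. **Sections 7.1 and 7.3.** State one ascertainment rule, with the same fixed wording at every contact in both arms, covering psychiatric change and including a brief question on any hospital admission.

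The cost is rewording three sections and adding one line to the form. Assuming about a minute per contact, eight sessions and the post-treatment visit add about 9 × 1 = 9 minutes per participant. A few more unrelated medical events will be recorded. The therapist still completes the form, so this removes the conflicting instructions but not the possibility of recording influenced by knowledge of the arm.

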7.5 Follow-up for Adverse Events

The clinical course of each event will be followed until resolution, stabilization, or until it has been determined that the study treatment or participation is not the cause. Serious adverse events that are still ongoing at the end of the study period will be followed up to determine the final outcome. Any serious adverse event that occurs after the study period and is considered to be possibly related to the study treatment or study participation will be recorded and reported immediately.

7.6 Safety Monitoring

This project will be monitored by an Independent Monitoring Committee. Refer to Data and Safety Monitoring Plan.

8. INTERVENTION DISCONTINUATION

An intervention can be discontinued if the participant chooses to do so or if the therapist or [name] believes it is in the participant's best interest. If the therapist or [name] judges that a subject requires a different approach or higher intensity care, the subject will be provided with referrals for outpatient or inpatient care, as appropriate. Participants will be asked to complete the all remaining assessments if they discontinue early.

9. STATISTICAL CONSIDERATIONS

9.1 General Design Issues

This project is a feasibility and proof of concept study of compassion meditation (CM) for Veterans with posttraumatic stress disorder (PTSD; $N \approx 100$). Phase 1 ($N \approx 60$, nonrandomized, Protocol Refinement, will consist of up to 4 CM and 2 Relaxation groups with 6-12 participants in each group. Iterative refinement of the treatment protocols will be done based on quantitative and qualitative data from participants. Phase 2 ($N \approx 40$), Pilot Evaluation is a randomized controlled study with 4 groups (2 CM and 2 relaxation groups, 6-12 in each group) to examine the feasibility of a randomized trial and to estimate response to CM. The study is not hypothesis driven, but rather developmental in nature.

The primary outcome measures in Phase 1 (see section 6.2) are related to refinement of the intervention, i.e., participants' behavior and reactions to the material and change in processes that are believed to be modified by CM (i.e., positive emotion, social connectedness, self-compassion). The primary outcome measures in Phase 2 (refer to section 6.2) are related to estimating the amount of change in symptomatology, functioning and psychological processes thought to be associated with CM.

9.2 Sample Size and Randomization

For Phase 1, we estimated sample size based on past experience in intervention development; we believe that we will need to run 4 CM groups to achieve Phase 1 refinements (e.g., [name], Norman, & [name], 2006). For the relaxation protocol, which was used in a prior PTSD study, we will begin with our modified version and expect 2 groups will be sufficient given the very minor modification. We will aim for a group size of 6-12, which can be recruited within the 1-month period we have allocated to recruitment before each group. Thus, we estimate that 60 people will take part in Phase 1 of the research.

In Phase 2, we will conduct a pilot study with 4 groups (2 CM and 2 relaxation groups, 6-12 in each group) to examine the feasibility of a randomized trial and response to CM. Thus, we anticipate approximately 40 participants in the second phase

Treatment Assignment Procedures

In phase 2, groups will be randomly assigned a treatment condition in a 1:1 ratio. The assessor will remain blind to these assignments; the study team will be careful not to disclose which group or therapist is seeing a given participant and participants will be asked to refrain from discussing the nature of their intervention during assessments. There is no need for breaking blind as treating clinicians will be aware of the treatment assignment.

9.3 Definition of Populations

Participants in both phases will be Veterans with PTSD who are able to consent and willing to participate. Co-occurring disorders such as depression, anxiety, or treated substance abuse or dependence problems are permitted provided that PTSD is the primary presenting complaint. Sixty people will take part in Phase 1 of the research and approximately 40 participants in the second phase, for a total sample size of approximately 100 people. This is intent to treat protocol and all subjects will be included in the study data analysis.

9.4 Interim Analyses and Stopping Rules

Not applicable

9.5 Outcomes

9.5.1 Primary Outcome

The primary outcomes of Phase 1 are participant reactions to the group (credibility, satisfaction, attendance, practice compliance, and weekly qualitative and quantitative feedback) as well as variables that reflect changes that are expected with practice of CM (positive emotion, social connectedness, self compassion). These includes: Client Satisfaction Questionnaire, credibility score, modified Differential Emotions Scale, time spent in and reactions to daily practice, reactions to group, short form of the Self Compassion Scale and Social Connectedness Scale. Refer to section 6.2 for the schedule of administration and descriptions of measures.

The primary outcome of Phase 2 is the CAPS-5, which quantifies PTSD symptomatology.

9.5.2 Secondary Outcomes

The secondary outcomes of Phase 1 are the rate of study enrollment based on various types of recruitment strategies as well as gender.

The secondary outcomes of Phase 2 include symptoms that frequently co-occur with PTSD (Brief Symptom Inventory, PROMIS measures of pain intensity, pain interference, sleep disturbance and sleep-related impairment), functioning/quality of life (Sheehan Disability Scale and Satisfaction with Life) as well as variables that capture the mechanisms by which CM may create change, including positive emotion (modified Differential Emotions Scale), social connectedness (Social Connectedness Scale), self-compassion (Short form of the Self Compassion Scale) and mindfulness (Philadelphia Mindfulness Scale).

9.6 Data Analyses

Although majority of data will be quantitative, some qualitative data also will be collected. [name] has experience with qualitative coding and analyses. [name] also has been added to the study team for her experience with qualitative interviewing, coding and analyses. We will analyze qualitative data using atlas.ti, a qualitative data analysis software package. Qualitative data analysis starts with coding, a process in which quotes are marked and labeled. The labeled quotes are then sorted and grouped, so that categories, then concepts, then themes can be developed. As is often standard practice for qualitative data analysis, analysis will be concurrent with data acquisition.

Quantitative data will be analyzed using SPSS version 18. These data will be examined initially for missing values. The primary aims of our data analytic strategy in phase 1 will be directed toward the development of CM and collection of data that will inform modification of the interventions. In phase 2 it will be directed toward examining the feasibility of CM. We would like to emphasize that, although we aim to estimate effect sizes to assist in future power calculations, this is not our major focus. Recent work by Kraemer (2006) has highlighted important limitations of this aim due to the large standard error surrounding the pilot study effect size. As a result, we will focus our analyses on a feasibility of conducting a larger CM study and report our findings with this limitation in mind. Our goal is to collect important data regarding the development of CM protocols, our ability to implement recruitment strategies, and the feasibility of the treatment and measurements. Information derived from our research will lead

to better-designed full-scale studies and informs decisions regarding whether it is worthwhile to commit additional resources to future CM treatment development. Due to our small sample size our statistical analytical findings should be interpreted with caution.

For quantitative data, descriptive statistics will be used to summarize the variables as well as to detect outliers and data entry errors. When applicable, normality of the distribution will be examined for outcome variables with a normal probability plot. HRV measures will be generated from heart rate data per the recommendations of the Task Force of the European Society of Cardiology and the North American Society of Pacing and Electrophysiology (Task Force, 1996). Chi- squares and Analysis of Variance will be used to assess the effectiveness of the randomization procedures by comparing participants in each treatment condition on baseline variables. Although there are important limitations associated with the analysis of our phase 2 data, we do propose to conduct limited statistical analyses. First, keeping in mind the theoretical and practical issues reviewed above, all analyses will be considered preliminary. We will calculate an estimated effect size for our primary outcome, though it will be interpreted with caution, and in the context of the 95% confidence interval that surrounds it. It will also be interpreted within the context of other important information such as the clinical significance of study findings, and existing data from prior relevant research studies.

Primary analyses will assess whether CM is superior to Relaxation. The two groups will be compared on CAPS, BSI, SDS and Philadelphia Mindfulness Scale using analysis of variance. We are also particularly interested in evaluation of patterns of missing data, dropout rates, distributional properties of variables, and correlations among measures. Missing data will be examined to assess randomness. The pattern of missing data will be examined according to the procedure recommended by Little and Rubin (1987), which includes comparing group differences in the primary outcomes of subjects with versus without missing data. We will test whether the drop-outs are random or systematic by comparing the drop-outs with the study completers on the baseline data. An absence of significant differences would support the random nature of drop- outs. Dropout rate will be compared between the groups using chi-square analysis. Given the limited sample size, multiple linear regression may be used carefully to examine whether group assignment predicts PTSD symptom severity at the follow-up assessment while controlling for initial values. Other potential covariates will include baseline demographic or clinical variables (e.g., concomitant medication use) that are not equivalent between the two treatment groups. Effect size for the difference between groups will be calculated according to procedures described by Cohen (1988). We will also explore the effect of patterns of missing data using Mixed Effects models (random regression models). We will perform sensitivity analyses for the impact that potentially informative missing data and dropout may have on the analyses. The mixed effects framework is robust with respect to drop-out and missing data, unless the drop-out mechanism or cause of missing is informative. We will use pattern-mixture models to assess if there is bias due to drop out or missing data.

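### The plan gives two competing accounts of what is primary in Phase 2: CAPS-5 alone (9.5), or a broader set that 9.6 lists as CAPS, BSI, SDS and the Philadelphia Mindfulness Scale (9.1 with 9.6)

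*Combined protocol and SAP*

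**What the plan says.** Four places in the combined protocol and SAP bear on this.

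- **9.5.1 Primary Outcome:** "The primary outcome of Phase 2 is the CAPS-5, which quantifies PTSD symptomatology". One outcome is named.
- **9.5.2 Secondary Outcomes:** BSI appears in "The secondary outcomes of Phase 2 include symptoms that frequently co-occur with PTSD (Brief Symptom Inventory, PROMIS measures", SDS in "functioning/quality of life (Sheehan Disability Scale and Satisfaction with Life", and the mindfulness scale in "mindfulness (Philadelphia Mindfulness Scale".
- **9.6 Data Analyses:** the paragraph on effect size refers to a primary outcome in the singular and plans an effect size with a 95% confidence interval for it. The next paragraph begins "Primary analyses will assess whether CM is superior to Relaxation. The two groups will be compared on CAPS, BSI, SDS and Philadelphia Mindfulness Scale" and names analysis of variance as the method.
- **9.1 General Design Issues:** "The primary outcome measures in Phase 2 (refer to section 6.2) are related to estimating the amount of change". The sentence goes on to name symptomatology, functioning and psychological processes.

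The plan also limits how much weight its results should carry. Section 9.1 states: "The study is not hypothesis driven, but rather developmental in nature". Section 9.6 says that estimating effect sizes is not the main focus and that every analysis is to be regarded as preliminary.

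**The concern.** Two accounts of the Phase 2 primary analysis stand side by side, and neither is marked as overriding the other. Suppose the arms differ on BSI, SDS or mindfulness but not on CAPS-5. Under 9.6 that could be reported as a primary-analysis finding of superiority; under 9.5 it is a secondary result. Because both readings are in the approved text, the choice could be made after the results are seen.

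This matters even in a pilot. Section 9.6 says the findings will inform whether further resources go into developing CM, so it matters which result is presented as the main one. Calling the analyses preliminary lowers the weight of any result, but does not say which result is primary.

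**Working it through.** **Step 1: compare the passages.**

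| Place | What is primary in Phase 2 | Status of BSI, SDS, mindfulness |
|---|---|---|
| 9.5.1 and 9.5.2 | CAPS-5 | Secondary |
| 9.6, effect-size paragraph | One outcome (singular) | Not mentioned |
| 9.1 | Measures of symptoms, functioning and psychological processes | Consistent with primary |
| 9.6, superiority comparison | CAPS, BSI, SDS, Philadelphia Mindfulness Scale | Under the primary-analyses label |

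The first two rows agree with each other, and so do the last two. The 9.6 list maps onto 9.1: CAPS and BSI are symptoms, SDS is functioning, mindfulness is a psychological process. The difference between 9.1 and 9.5.1 is thus one of content and goes beyond singular against plural.

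**Step 2: check whether the 9.6 list could simply mean all outcomes.** Section 9.5.2 names BSI (1), PROMIS pain intensity, pain interference, sleep disturbance and sleep-related impairment (4), SDS (1), Satisfaction with Life (1), mDES (1), Social Connectedness (1), Self Compassion (1) and Philadelphia Mindfulness (1). That is 1 + 4 + 1 + 1 + 1 + 1 + 1 + 1 = 11. The 9.6 list is CAPS plus 3 of these 11 and leaves out 11 − 3 = 8, so it is neither the primary list nor the full list of 9.5.

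**Step 3: illustrate the size.** The plan states no significance level, power or correlation for Phase 2, so it has no figure to reproduce. Assumptions, none from the documents: two-sided 0.05, so 0.025 in the direction favouring CM (critical value c = 1.96); normal test statistics with equal correlation ρ, all four scored so that positive means benefit; no clustering.

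Chance of at least one false positive favouring CM among four scales:

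- For ρ = 0: 1 − (1 − 0.025)^4 = 1 − 0.9037 = 0.0963.
- For ρ > 0: 1 − ∫ Φ[(c − √ρ·z)/√(1 − ρ)]^4 φ(z) dz, by numerical integration.

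| ρ | CAPS-5 alone | Any of four | Only on a 9.5.2 secondary scale | Ratio |
|---|---|---|---|---|
| 0 | 2.5% | 9.6% | 9.6 − 2.5 = 7.1% | 0.0963/0.025 = 3.85 |
| 0.5 | 2.5% | 7.8% | 7.8 − 2.5 = 5.3% | 0.0779/0.025 = 3.12 |
| 0.7 | 2.5% | 6.5% | 6.5 − 2.5 = 4.0% | 0.0652/0.025 = 2.61 |

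The fourth column is the share of null trials in which the only result that could be called primary is on a scale that 9.5.2 calls secondary.

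**The case against.** The best defence is that 9.5 exists to define outcomes and is clear, and that the effect-size paragraph of 9.6 agrees with it. On this view the primary-analyses label means the main between-arm comparisons, as opposed to the missing-data, regression and sensitivity work later in the same paragraph. That reading is possible but not the natural one. The four-scale sentence follows the superiority sentence directly, is the first to say how superiority will be assessed, and has no secondary label in between. The reading also leaves 9.1 unexplained.

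The second defence is that this is a developmental pilot with preliminary analyses and no stated significance level or success rule. This stands, and it limits the harm.

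Three stronger readings might tempt a reader, and the documents do not support them.

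- **A failed confirmatory error rate that needs a multiplicity correction.** The plan makes no confirmatory claim and states no significance level. Relabelling would not reduce the number of tests; it only fixes which result may be called primary.
- **The plural in the missing-data sentence as further proof.** Section 9.6 refers to "comparing group differences in the primary outcomes of subjects with versus without missing data". But 9.6 covers both phases, and Phase 1 has several primary outcomes under 9.5.1, so the plural may be correct.
- **Larger figures from therapy-group clustering.** With an assumed intraclass correlation of 0.05, two groups of 10 per arm and an analysis that ignores groups, simulated four-scale chances are 19.6%, 15.2% and 12.8%, against about 5.3%, 5.2% and 5.2% for CAPS-5 alone. The ratios, 19.6/5.3 = 3.7, 15.2/5.2 = 2.9 and 12.8/5.2 = 2.5, are no higher than without clustering. That inflation is a separate matter and adds nothing to the labelling point.

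**Conclusion.** The conflict is real and can be read from the text without any calculation: 9.5 and the effect-size paragraph of 9.6 point to CAPS-5 alone, while 9.1 and the superiority comparison in 9.6 point to a broader set. It should be resolved before analysis, so that the primary label cannot be assigned according to the results.

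The consequence is modest. Under the assumptions given (two-sided 0.05, equal correlation from 0 to 0.7, no clustering), the chance of a false-positive result that could be called primary and favours CM is about 2.6 to 3.9 times that for CAPS-5 alone. These figures illustrate the room for selective labelling; they are not error rates that the plan undertook to control.

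**What to change.** Follow 9.5, the section that defines the outcomes.

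1. **9.6, superiority comparison.** Replace the two sentences with text such as: *The primary Phase 2 analysis will test whether CM is superior to Relaxation on CAPS-5. BSI, SDS and the Philadelphia Mindfulness Scale will be compared between arms as secondary analyses.* Retain the superiority aim, the planned methods (analysis of variance, with the optional baseline-adjusted regression), the 95% confidence interval and the preliminary status.
2. **9.1, Phase 2 sentence.** Replace with: *The Phase 2 primary outcome measure is the CAPS-5; secondary outcome measures cover co-occurring symptoms, functioning and quality of life, and psychological processes (see 9.5).*
3. **Missing-data sentence in 9.6.** Leave unchanged, because it may cover Phase 1.

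The cost is two edits to wording. Data collection and methods are unaffected. The sponsor gives up the primary label on three scales that 9.5.2 already calls secondary.

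If the sponsor in fact meant the broader version in 9.1 and 9.6, then 9.5 must be changed to match, and this must be done before any Phase 2 data are analysed.
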